- To assess the rate of relapse (timeframe for assessing relapse - between EoT and SVR 12)
- To describe baseline characteristics of patients with HCV Gt1b and compensated cirrhosis treated with AbbVie 3D regimen.
- To collect information on co-morbidities and concomitant medications in cirrhotic patients in the Russian population
- To describe the tolerability of the ABBVIE REGIMEN

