No data will be imputed for any effectiveness or safety analyses except for the analyses of the HCV RNA endpoints. When there is no HCV RNA value in a visit time window post-baseline, but prior to EoT, the closest values before and after the window, regardless of the value chosen for the subsequent and preceding window, will be used for the flanking imputation described below. If a patient has a missing HCV RNA value at a post-Visit 1

visit prior to EoT but has undetectable HCV RNA (with LLoD \leq 50 IU/mL) or unquantifiable, but detectable HCV RNA levels (with LLoQ \leq 50 IU/mL) at both the preceding and succeeding measurements, the HCV RNA level will be considered undetectable or unquantifiable, respectively, at this visit for this patient. In addition, if a patient has an unquantifiable HCV RNA level at the preceding measurement and an undetectable HCV RNA level at the succeeding measurement, or vice versa, the HCV RNA level will be imputed as unquantifiable at this visit for this patient. For virological response at EoT a corresponding backward imputation approach will be applied. This means if HCV RNA is missing at EoT, then unquantifiable or undetectable will be assumed for EoT, if the succeeding HCV RNA value is undetectable or unquantifiable. For SVR12 the single last available HCV RNA measurement \geq 84 days post-treatment will be used. Subsequent to this flanking and backward imputation, if the HCV RNA value remains missing at a specific time point, then the patients will be considered as virological failure at this time point (i.e. not undetectable or unquantifiable).

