9.13.6 Statistical Methods for Analysis of Effectiveness Variables

The simple percentage of patients achieving SVR12 will be calculated and an exact two-sided 95% confidence interval (CI) of the percentage will be computed based on the Clopper-Pearson method.

Corresponding methods will be used for other response rates (EoT response rate, relapse rate). The relapse rates will be estimated in patients of the CP analysis groups with EoT response and sufficient HCV RNA measurements post-treatment.

These analyses will be of exploratory nature, data driven, and will be repeatedly performed for various CP Analysis Groups, since not each covariate might be predictive in each patient group. Furthermore, the fact that treatment regimens will differ in the various patient groups has to be taken into account, when selecting the patient groups for each MLR analysis. Backward selection procedures will be applied to generate the final MLR models which consider only covariates in the selection procedure with a p-value <0.25 in the corresponding univariate logistic regression analysis. A p-value <0.05 will be used for the covariates to stay in the model in a backward elimination step. Logistic regression methods will also be used to investigate the impact of treatment adherence on SVR12.

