7.5 Multiple comparisons

No adjustments for multiplicity are required.

8 Summary of study data

Each study variable will be analyzed for relevant population.

Unless otherwise specified all raw data will be listed and sorted by unique subject identifier and study period/assessment (i.e. time point), where applicable.

Demographic and baseline characteristics, concurrent illnesses and medical conditions, prior and concurrent medications will be reported for *the core population (CP)*.

The results will be presented overall and for the CP analysis groups based on genotype 1 subtype, fibrosis status and treatment experienced or naïve.

According to the eligibility criteria of this study¹, only patients with genotype 1b and Child Pugh A cirrhosis will be included in this study. In this way, the results will be presented for the CP analysis groups by the following parameters:

- cirrhosis score² (5 or 6);

- treatment experienced or naïve patients³ (with/without prior treatment for CHC).

Additionally demographic and baseline characteristics, concurrent illnesses and medical conditions, prior and concurrent medications will be reported for *the target population (TP)* and *the safety population (SP)* overall only (without the CP analysis grouping).

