 - relapse after EoT (HCV RNA value <50 IU/mL or undetectable/negative at EoT or at the last on-treatment HCV RNA measurement followed by HCV RNA \geq 50 IU/mL or positive post-treatment);
 - failure to suppress (each measured on-treatment HCV RNA value \geq 50 IU/mL or positive);
 - premature study drug discontinuation with no on-treatment virologic failure;
 - missing SVR12 data and/or none of the above criteria.

Figure 9.1 illustrates the patient's distribution by SVR12 response/non-response categories.

P16-253 (CITRIN) _ STATISTICAL ANALYSIS PLAN _ FINAL 2.0 _ 16 Mar 2018

[figure not shown]

Figure 9.1 – Patient's distribution by SVR12 response/non-response categories. Frequencies and percentages with 95% confidence intervals will be calculated for each effectiveness outcomes and will be presented according the section 7.1. Also frequency tables will be repeated for patients in subgroup without missing SVR12 data category.

Effectiveness endpoints (SVR12 achieving, virological response at EoT and relapse after EoT) will be analyzed using univariate logistic regression, if applicable. These analyses will be of exploratory nature, data driven, and will be repeatedly performed for various CP analysis groups, since not each covariate might be predictive in each patient group.

The following parameters can be included in the univariate models as explanatory variables (fixed effect or covariate):

- treatment experience (with/without prior treatment for CHC);
- Child Pugh score;
- result of FibroTest;
- history of liver decompensation;
- age;
- gender;
- race;
- BMI;
- laboratory hematology¹:
 - hemoglobin;
 - platelets;
 - prothrombin time;
 - laboratory clinical chemistry:
 - ALT;

¹ Note that all Hematology variables and all Clinical Chemistry should be in the same units. If it is impossible to bring units to the same the smallest units groups will be accepted as missing. If it is impossible to identify the smallest units groups the corresponding covariate will be deleted from the analysis.

P16-253 (CITRIN) _ STATISTICAL ANALYSIS PLAN _ FINAL 2.0 _ 16 Mar 2018

- AST;
- Gamma-GT;
- total bilirubin;
- albumin;
- creatinine clearance;
- alpha-1-fetoprotein.

Additionally, after univariate model analyses all effectiveness endpoints can be analyzed using MLR (if applicable) which consider only covariates in the selection procedure with a p-value <0.25 in the corresponding univariate logistic regression analysis¹.

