Table 1.13.3 Concurrent Medications for CHC (treatment-experienced groups)
Table 1.13.4 Concurrent Medications for CHC (Child Pugh score groups)

for the target and safety populations

Table 1.13.5 Concurrent Medications for CHC
Table 1.13.6 Concurrent Medications for CHC

P16-253 (CITRIN) _ STATISTICAL ANALYSIS PLAN _ FINAL 2.0 _ 16 Mar 2018
Effectiveness Analyses (TP)

 AbbVie Ltd
 P16-253

Table 2.1.1.1 Percentage for effectiveness endpoints

The target population (TP)

Page X of X

| Parameter Statistics | Total (N=XX) |
|---|------------------------------|
| | n (%) |
| | [95% CI] |
| SVR12 achieving (single last HCV RNA value <50 IU/mL 12 weeks after the last actual dose of the ABBVIE REGIMEN) | XX (XX.X) [XX.XX - XX.XX] |
| SVR12 non-response | XX (XX.X) [XX.XX - XX.XX] |
| Patients with breakthrough (at least one documented HCV RNA value <50 IU/mL followed by HCV RNA ≥50 IU/mL during treatment) | XX (XX.X) [XX.XX - XX.XX] |
| Failure to suppress (each measured on-treatment HCV RNA value ≥50 IU/mL) | XX (XX.X) [XX.XX - XX.XX] |
| Patients with relapse (HCV RNA value <50 IU/mL at EoT or at the last on-treatment HCV RNA measurement followed by HCV RNA ≥50 IU/mL post-treatment) | XX (XX.X) [XX.XX - XX.XX] |
| Patients with premature study drug discontinuation with no on-treatment virological failure (breakthrough or failure to suppress) | XX (XX.X) [XX.XX - XX.XX] |
| Patients with missing SVR12 data | XX (XX.X) [XX.XX - XX.XX] |
| Patients with virological response (HCV RNA <50 IU/mL) at EoT | XX (XX.X) [XX.XX - XX.XX] |

N: the number of subjects in the target population. n: number of subjects within a specific category. Percentages are calculated as 100 x (n/N).
 EoT: end of treatment. SVR12: sustained virological response at 12 weeks after EoT. 95% CI: 95% confidence interval (the Clopper-Pearson method).

Program code, date, time

Data extracted: DD.MM.YYYY

P16-253 (CITRIN) _ STATISTICAL ANALYSIS PLAN _ FINAL 2.0 _ 16 Mar 2018

 AbbVie Ltd
 P16-253

Table 2.1.2.1 Percentage for effectiveness endpoints without patients with missing SVR12 results
 The target population (TP)
 Page X of X

| Parameter Statistics | Total (N=XX) n (%) [95% CI] |
|---|--------------------------------------|
| SVR12 achieving (single last HCV RNA value <50 IU/mL 12 weeks after the last actual dose of the ABBVIE REGIMEN) | XX (XX.X) [XX.XX - XX.XX] |
| SVR12 non-response | XX (XX.X) [XX.XX - XX.XX] |

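### No SAP table gives the relapse rate that protocol 9.13.6 requires: EoT responders with sufficient post-treatment HCV RNA, by CP analysis group

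*SAP*

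**What the plan says.** Protocol 8.2.2 lists as a secondary objective: "To assess the rate of relapse (timeframe for assessing relapse - between EoT and SVR 12"). Protocol 9.13.6 sets the denominator: "The relapse rates will be estimated in patients of the CP analysis groups with EoT response and sufficient HCV RNA measurements post-treatment". The Data Analysis part of the protocol abstract repeats this and asks for SVR12, EoT response and relapse rates in the CP analysis groups, with Clopper-Pearson intervals. It then adds a second relapse denominator, namely all patients of those groups with undetectable HCV RNA at the EoT visit.

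SAP 9 plans frequencies and percentages with 95% intervals for each outcome on the target population (TP), the CP and the CP with sufficient follow-up (CPSFU). It adds: "Also frequency tables will be repeated for patients in subgroup without missing SVR12 data category". Shell Table 2.1.1.1 in SAP 18 has one Total column, with the footnote "N: the number of subjects in the target population. n: number of subjects within a specific category. Percentages are calculated as 100 x (n/N"). Shell Table 2.1.2.1 applies the same rule after removing patients with missing SVR12. The CP and CPSFU tables are built from these two shells, and the CPSFU pair is labelled as the main analysis.

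SAP 8 defines the CP analysis groups ("In this way, the results will be presented for the CP analysis groups by the following parameters") as cirrhosis score 5 or 6 and treatment-experienced or naïve. SAP 15 states that the SAP is fully consistent with the protocol.

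**The concern.** A relapse rate is a conditional quantity. Only a patient who had responded by EoT can relapse after it, and only a patient tested afterwards can be seen to relapse or not. Protocol 9.13.6 builds both conditions into the denominator. The SAP tables apply at most the second.

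The numerator differs as well. In SAP 9 and the shells, relapse may follow response at EoT or "at the last on-treatment HCV RNA measurement followed by HCV RNA" at or above the threshold. Under protocol 9.13.1, "if HCV RNA is missing at EoT, then unquantifiable or undetectable will be assumed for EoT, if the succeeding HCV RNA value is undetectable"; an unquantifiable value also suffices. A patient with no EoT value and a later positive one is therefore not an EoT responder. That patient can enter the SAP's relapse row but lies outside the 9.13.6 risk set.

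The report could thus print a relapse percentage for a secondary objective that is not the protocol's estimate, omit the CP-group rates altogether, and declare no departure. Readers could not tell how far the printed figure is from the intended one, because the risk set is not shown.

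**Working it through.** **1. Which outputs mention relapse.** I compared SAP 9, the table list in SAP 16 and the shells in SAP 18 with protocol 9.13.6.

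| Output | Denominator | EoT responders only? | CP-group columns? |
|---|---|---|---|
| Percentage tables, full set (TP, CP, CPSFU) | whole set | no | no |
| Percentage tables without missing SVR12 | set minus missing SVR12 | no | no |
| Relapse after EoT, logistic regression | no risk set stated; odds ratios and p-values | not stated | no rate given |
| Protocol 9.13.6 | EoT responders with sufficient post-treatment HCV RNA | yes | yes |

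The baseline tables in SAP 16 have versions by prior treatment and by Child Pugh score. The effectiveness percentage tables have none.

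**2. Interval method.** For x events in n, the two-sided 95% Clopper-Pearson limits are the 0.025 quantile of Beta(x, n−x+1) and the 0.975 quantile of Beta(x+1, n−x). The documents give no relapse figure to reproduce. As a check, 60/60 gives a lower limit of 0.025^(1/60) = 94.04%, which agrees with the 94.0% that protocol 7.0 quotes for the previous 60-patient study.

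**3. Assumed counts.** Only the study size of 60 comes from the documents (protocol 9.11). I assume that all 60 are in the CP, with 58 EoT responders and 2 EoT non-responders. Of the responders, 50 have an SVR12 measurement and 8 are untested for reasons unrelated to safety or effectiveness. Then:
- companion table and CPSFU: 60 − 8 = 52;
- 9.13.6 risk set: 58 − 8 = 50;
- abstract's second denominator: 58.

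| Denominator | 2 relapses, both EoT responders (95% CI) | 0 relapses, upper limit |
|---|---|---|
| Full CP, n = 60 | 3.33% (0.41–11.53) | 5.96% |
| Companion or CPSFU, n = 52 | 3.85% (0.47–13.21) | 6.85% |
| 9.13.6 risk set, n = 50 | 4.00% (0.49–13.71) | 7.11% |
| Abstract's second, n = 58 | 3.45% (0.42–11.91) | 6.16% |

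The gap to the 9.13.6 rate is 4.00 − 3.33 = 0.67 percentage points for the full set and 4.00 − 3.85 = 0.15 for the companion or CPSFU table. With no EoT non-responders, the latter gap is zero. If 55 responders are tested, the three rates are 2/60 = 3.33% (upper 11.53), 2/57 = 3.51% (12.11) and 2/55 = 3.64% (12.53).

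**4. Direction.** If one of the two relapsers had no EoT response, the SAP prints 2/60 = 3.33% or 2/52 = 3.85%, while the 9.13.6 rate is 1/50 = 2.00% (upper 10.65). If the abstract's second denominator governs, the target is 2/58 = 3.45%, above the full-set figure but below the companion and CPSFU figure.

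**5. One CP analysis group** (assumed 30 patients, 1 EoT non-responder, 4 untested, 1 relapse): 1/30 = 3.33% (upper 17.22), 1/26 = 3.85% (19.64), 1/25 = 4.00% (20.35). With no relapse the upper limits are 11.57%, 13.23% and 13.72%. The SAP plans none of these group figures.

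**The case against.** The strongest reply is that little is lost. The study is descriptive, with no hypothesis test or sample-size target. On the assumed counts the gap is 0.15 points in the tables labelled as main analysis, against intervals about 13 points wide. The tables print both the relapse and the EoT-response counts, so a reader could approximate the overall rate. This stands as a limit on size. It does not supply an interval or any group figure, and the relapse count need not lie within the EoT responders.

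A second reply is that both documents already define sufficient follow-up through CPSFU, so the word in 9.13.6 has a natural meaning. That is a fair reading and the fix uses it. CPSFU still includes EoT non-responders, so the CPSFU tables are not the 9.13.6 rate.

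A third is that the protocol itself is unsettled, because its abstract gives two denominators. True, but both condition on EoT response and the SAP's do not.

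SAP 7.1 bases percentages on non-missing data only by default, and the shells override it with n/N. The group results promised in SAP 8 concern baseline, co-morbidity and medication data. SAP 9 mentions the groups only for regression.

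A reader might infer that the SAP materially understates relapse, or that the n/N row is itself an error. The documents support neither. The direction is not fixed, and the row is valid as an SVR12 non-response category under protocol 9.13.5.

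**Conclusion.** The point holds as a mismatch between protocol and SAP on a named secondary objective, and it should be corrected. No planned table reports relapse on the risk set of 9.13.6, none gives a relapse rate by CP analysis group, and SAP 15 does not disclose the difference. With the same numerator, the SAP figure is at or below the 9.13.6 rate, by 0.15 to 0.67 percentage points with 50 responders tested. It can lie above that rate if some relapsers lack EoT response, and the companion or CPSFU figure can lie above the abstract's second rate. These sizes rest entirely on assumed counts. The absence of the conditional rate, its interval and the group results follows from the documents alone.

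**What to change.** In the CP effectiveness tables, add a row for relapse after EoT with its own printed denominator. It should contain patients with EoT response, after the protocol 9.13.1 imputation, who have one of the following:

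- (a) HCV RNA at least 84 days after the last dose, as in protocol 9.13.1 and 9.13.4;
- (b) a documented post-treatment value of at least 50 IU/mL or positive;
- (c) a relapse reported in the eCRF with its date or value missing, counted as relapse.

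Clause (c) matters. Protocol 9.13.1 and SAP 6 keep such patients in CPSFU. Without the clause, one such patient among the two relapsers would turn 2/50 = 4.00% into 1/49 = 2.04% (upper 10.85).

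State that the row follows the protocol's 84-day rule and not the window of 57 to 112 days in SAP Table 4.2, under which an early negative could count as relapse-free. State also that this is the CPSFU notion of sufficient follow-up restricted to EoT responders, without those whose last value was negative and who left for safety reasons untested at 84 days.

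Count in the numerator only patients in that denominator, compute Clopper-Pearson on it, and footnote relapsers left out for lack of EoT response. Keep the n/N row, labelled as an SVR12 non-response category. SAP 9 plans: "Effectiveness endpoints (SVR12 achieving, virological response at EoT and relapse after EoT) will be analyzed using univariate logistic regression, if applicable". Any relapse regression should use the new risk set.

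Add columns by prior treatment and Child Pugh score (5 or 6) for SVR12, EoT response and relapse, because the abstract and protocol 9.13.3 want all three by group. Record in SAP 15 that 9.13.6 is followed and not the abstract's second denominator; the latter may be shown as a sensitivity row. No separate CPSFU row is needed. As a separate correction, >50 IU/mL at EoT in the SAP 3.2 definition of relapse should read <50 IU/mL.

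The cost is one row and footnote, extra columns, a short definition in SAP 9 and one entry in SAP 15. No new data are needed. Group intervals will be wide.
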